8. ASSESSMENT OF APVO101 EFFICACY

8.1. Subject's Assessment of Efficacy

Throughout the study, subjects and/or their parent or legal guardian will maintain a subject diary to record information about each APVO101 infusion, any AEs and all bleeding episodes (trauma or spontaneous). An assessment of efficacy will be made for each bleeding episode. In the event of trauma, details will be recorded.

Within 6 hours (exact time to be recorded) after the subject believes the bleeding has stopped, an overall evaluation of efficacy of treatment will be provided. This will be done using the following verbal descriptors:

- Excellent: a dramatic response with abrupt pain relief and clear reduction in joint or hemorrhage site size
- Good: pain relief or reduction in hemorrhage site size that may have required an additional infusion for resolution
- Fair: probable or slight beneficial response usually requiring one or more additional infusions for resolution
- Poor: no improvement or condition worsens

In addition to the description of efficacy, the subject and/or their parent or legal guardian will indicate the following:

- How long it took the bleeding to stop
- How long it took the pain to stop
- How long it took the swelling (if present) to resolve

This will be done for each variable using a series of check boxes for time intervals ranging from < 2 hours to 72+ hours after the onset of the bleeding episode.

The study investigator will be contacted by the subject, if efficacy of two consecutive APVO101 infusions is rated as 'fair' or 'poor'. The subject will be instructed to call the treatment center if there is an occurrence of 'poor' or no response to the therapy (i.e., sub-optimal response; see [Section 8.2](#)) for a specific bleeding episode.

The subjects and/or their parent or legal guardian will document in the diary if no bleeding episodes occurred.

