8.2. Investigator's Assessment of Efficacy

At each study visit [during Treatment Phase and Continuation Phase; see Table 1], the investigator will make an assessment of APVO101 prophylaxis efficacy and an assessment of efficacy for control of bleeding episodes [if bleeding episode(s) are reported by the subject and/or their parent or legal guardian during the period]. The assessment will be based on the recording of events in the diary (i.e., review of subject diary) and discussion with the study subject and/or their parent or legal guardian.

The investigator will indicate the overall assessment of APVO101 prophylaxis efficacy, considering the absence of bleeding episodes, site, severity and types of bleeding episodes treated, and other factors that might influence the therapeutic response. In addition, when bleeding episode(s) are reported by the subject and/or their parent or legal guardian, the investigator will also rate the APVO101 efficacy for control and management of bleeding episode(s) treated. The investigator will consider the site, severity and type of the bleeding episodes reported by the subject and/or their parent or legal guardian when evaluating efficacy of APVO101 for control and management of bleeding episodes.

The investigator's efficacy assessment categories for prophylaxis and control of bleeding episodes will include: 'effective', 'partially effective' and 'not effective'.

If, in the estimation of the investigator, the response has been sub-optimal (i.e., an occurrence of 'poor' or 'no response' to the therapy for a specific bleeding episode as reported by the subject and/or their parent or legal guardian), this will be recorded and the reason for this assessment will be specified. In such an event (sub-optimal response), the investigator will review the circumstances surrounding the bleed and its response to therapy. Information collected shall include the following:

- Site of the bleed
- Cause and extent of injury
- Past history of bleeds at the anatomical site (determined by the investigator from subject's medical and hemophilia-related history and from the review of subject's diary while on study)
- Relevant clinical issues at the site for that bleed (e.g., in the case of a joint bleed, if the joint is a target joint, the extent of pain, joint swelling, and dysfunction over time (determined by the investigator from subject's medical and hemophilia-related history)
- Specifics of the management administered to that point

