10. ANALYTICAL PLAN AND STATISTICAL METHODS

10.1 GENERAL CONVENTIONS AND STATISTICAL CONSIDERATIONS

All statistical analyses will be performed and data appendices will be created using the SAS system version 9.4 or higher.

Data collected in this study will be presented in summary tables and subject data listings. Unless otherwise specified, all data will be summarized overall and by age group (<6 years and 6 to <12 years).

Subjects in the younger age group must remain < 6 years age throughout the treatment period (at least 50 ED) and the upper age group must remain < 12 years throughout the treatment period (at least 50 ED).

Descriptive statistics (number of non-missing values, mean, standard deviation [SD], median, first quartile [Q1], third quartile [Q3], minimum and maximum) will be presented for continuous variables. The number of decimal places in mean, median and quartiles will be equal to number of decimal places in the data + 1, decimal places in standard deviation = decimal places in the data + 2, number of decimal places in minimum/maximum will be equal to number of decimal places in the data.

Frequency distributions (counts and percentages) will be presented for categorical variables. If not specified otherwise, the number of observations with non-missing values will be the denominator for percentage calculation. Percentages will include one decimal place except for 100% where no decimal places will be provided.

By-visit and by-study phase summaries will be presented using nominal eCRF visits (which can be up to ± 5 ED to actual exposure days, see section 15)

All data collected will be presented in the data listings. Missing parts of the partial dates will be represented with dashes in the listings.

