10.7.2 ANALYSIS OF SECONDARY EFFICACY ENDPOINTS

Both types of secondary efficacy endpoints (bleeding episode level and subject level) will be presented descriptively for the Treatment Phase (bleeding episodes and subject level assessments occurred from first dose to 50 ED up to 3 days after last dose of APVO101 given for prophylaxis), Continuation Phase (bleeding episodes and subject level assessments occurred on or after first dose after 50 ED given for prophylaxis) and overall (all bleeding episodes and subject level assessments in a subject).

Summaries for bleeding episode level endpoints will include:

- Number and percentage of bleeding episodes within each category of subject's rating of efficacy;
- Number and percentage of bleeding episodes within each category reported by subjects as answer to question "How long did it take for the pain to stop?"
- Number and percentage of bleeding episodes within each category of highest level of pain during the bleeding episode.
- Number and percentage of bleeding episodes within each category reported by subjects as answer to question "How long did it take for the swelling to go down?"
- Descriptive statistics for time from onset of bleeding to the first infusion (minutes) as continuous variable

- Descriptive statistics for time from onset of treatment until resolution of the bleeding episode (minutes) as continuous variable
- Descriptive statistics for number of infusions required to treat the bleeding episode as continuous and categorical variable

Note: a bleeding episode which occurred after PK dose but prior to completion of PK assessment will be included into ABR calculations.

Summaries for subject level endpoints will include by-visit summaries for the following Investigator's assessments:

- APVO101 prophylaxis efficacy assessment
- Efficacy for control of bleeding episodes assessment

All data for subject assessments of bleeding episodes and Investigator assessments of efficacy will be listed.

10.7.3 ANALYSIS OF EXPLORATORY EFFICACY ENDPOINTS:

The following endpoints related to surgery will be summarized as frequency variables:

- Pre- and Post-surgery assessments:
 - Surgeon's assessment of total blood loss
- 12 hours (± 3 hours) post-surgery assessment and 24 hours (± 3 hours) post-surgery assessment:
 - Surgeon's assessment of total blood loss
 - Surgeon's assessment of APVO101 hemostatic efficacy

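### The subject's efficacy rating is timed to the end of the bleed and its percentages leave out unrated bleeds, which may favour the product

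*Protocol*

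**What the plan says.** Protocol 8.1 intends full coverage: "An assessment of efficacy will be made for each bleeding episode". The overall rating on the four-level scale has one stated time, within 6 hours "after the subject believes the bleeding has stopped, an overall evaluation of efficacy of treatment will be provided". The lowest level is "Poor: no improvement or condition worsens".

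The same section has two contact rules. The investigator is contacted "if efficacy of two consecutive APVO101 infusions is rated as 'fair' or 'poor". Separately, "The subject will be instructed to call the treatment center if there is an occurrence of 'poor' or no response to the therapy". Under Protocol 8.2, when the investigator judges a response sub-optimal, "this will be recorded and the reason for this assessment will be specified".

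SAP 10.7.2 reports the rating as "Number and percentage of bleeding episodes within each category of subject's rating of efficacy". SAP 10.1 supplies the default that, unless stated otherwise, "the number of observations with non-missing values will be the denominator for percentage calculation". SAP 10.3 has missing-data rules for adverse event attributes and dates only, and none for a missing efficacy rating.

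**The concern.** The event that prompts the rating is the family's belief that the bleeding is over. A bleed that responds reaches that point quickly. One that does not respond reaches it late, or not at all while the child is on study. One route to the second case is in the protocol itself: under 8.2 a child with a confirmed inhibitor is withdrawn, and a bleed open at that moment may never be rated. Whether a rating exists can therefore depend on the outcome that it measures, and the default denominator then removes the unrated bleed without showing it.

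Control of hemorrhaging is part of a primary objective. The primary endpoint, the annualized bleeding rate (ABR), counts bleeds and says nothing about how well they were controlled. That part of the objective rests on the secondary endpoints, and this rating is listed first among them.

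A related inconsistency concerns the first contact rule. It refers to ratings of individual infusions, but Protocol 8.1 defines only one overall rating per bleed, given after it ends, and SAP 10.7.2 summarises no infusion-level rating.

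**Working it through.** The plan gives no expected rating distribution, missing-rating rate or target precision, so there is no figure of its own to reproduce. The check has four steps.

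**1. Which bleeds enter the percentage.** The summary in SAP 10.7.2 names no denominator, so the SAP 10.1 default applies. A treated bleed with no rating is in neither numerator nor denominator.

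**2. Size and direction of the effect.** Let r be the Excellent/Good share among rated bleeds, u the fraction of treated bleeds without a rating, and q the share of those unrated bleeds that would have been Excellent/Good.

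- Share over all treated bleeds = (1 − u)·r + u·q
- Rated-only share minus all-bleeds share = u·(r − q)

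The difference is zero if u = 0 or q = r, positive if unrated bleeds did worse, and negative if they did better. With assumed values r = 80% to 90% and the worst case q = 0:

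- u = 5%: 4.0 to 4.5 percentage points
- u = 10%: 8.0 to 9.0 points
- u = 20%: 16.0 to 18.0 points

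**3. How many bleeds to expect.** Protocol 1.2.2 gives median ABRs on prophylaxis of 0.3 (IB1001-02, pediatric) and 1.52 (IB1001-01, mainly adolescents and adults). Protocol 3.3 aims for 15 to 20 evaluable children, and Protocol 3.1 expects at least 12 months per child. Using the medians as rates, for 20 children over 1 year (assumptions):

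- 20 × 0.3 × 1 = 6 bleeds
- 20 × 1.52 × 1 = 30.4, about 30 bleeds

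SAP 10.1 also splits results by age group. With 10 children per group, the counts are about 3 and 15.

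**4. What one unrated failure does if every other bleed is Excellent/Good.**

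| Treated bleeds | All treated bleeds | Rated only | Difference |
|---|---|---|---|
| 6 | 5/6 = 83.3% | 5/5 = 100% | 16.7 points |
| 30 | 29/30 = 96.7% | 29/29 = 100% | 3.3 points |
| 3 (one age group) | 2/3 = 66.7% | 2/2 = 100% | 33.3 points |
| 15 (one age group) | 14/15 = 93.3% | 14/14 = 100% | 6.7 points |

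The first row agrees with step 2: u = 1/6, r = 1 and q = 0 give 16.7 points.

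The opposite direction is also possible. If 6 bleeds are treated, 4 of the 5 rated are Excellent/Good, and the unrated one resolved quickly and would have been Excellent/Good, the rated-only figure is 4/5 = 80.0% against 5/6 = 83.3%. The plan then understates control by 3.3 points.

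**The case against.** The strongest reply is that an end-of-bleed rating suits this scale. 'Good' and 'Fair' both refer to further infusions needed for resolution, so neither can be fully judged before the bleed resolves. The protocol asks for an assessment of every bleed, most bleeds eventually stop, and a family can then give 'Poor' in retrospect. Control is also described by infusions per bleed, time to resolution, and an investigator rating that includes a 'not effective' level and draws on discussion as well as the diary. All individual assessments are listed, everything is descriptive, and the table shells are in a separate document that may already have a 'not rated' row.

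Much of this stands, and it rules out three stronger readings.

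- A reader might infer that 'Poor' cannot be recorded. The documents do not bar it: a retrospective 'Poor' is allowed.
- A reader might infer that the sub-optimal response review must wait until the bleed ends. The call to the center also covers no response to therapy, which is not a level of the scale and needs no completed rating.
- A reader might infer that the rating should move to a fixed time after infusion. That would leave 'Good' and 'Fair' hard to assign. The diary's time boxes run from bleed onset, not from infusion. The change would also need a formal amendment under Protocol 13.2 in a trial already under way, and would mix two timings among few bleeds.

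The reply does not remove the gap in the summary. Asking for a rating of every bleed is not a rule for a bleed that lacks one. Listings do not correct a percentage, and a row in an unseen shell would not change the denominator written in the SAP. Time to resolution is summarised as an ordinary continuous variable with no stated handling of bleeds that do not resolve.

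**Conclusion.** The point holds as a gap in the rules and a risk of bias. The rating is tied to perceived cessation, no rule covers unresolved or unrated bleeds, and the default denominator drops them. This may favour the product, because non-response is a plausible reason for a missing rating. A reader might infer that the bias is always favourable, but the documents do not support that: it is zero or reversed under the conditions in step 2 of the check, and they give no data on how many bleeds go unrated or how those bleeds fared.

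With about 6 to 30 bleeds, one unrated failure moves the overall result by 16.7 to 3.3 points, and by more within an age group. These figures assume 20 children, 1 year each, medians used as rates, and that the one unrated bleed is a failure. Follow-up may be longer than 12 months, and a median need not equal the mean rate. More bleeds would make the effect of one unrated bleed smaller.

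The contact rule based on two consecutive infusion ratings and the single rating per bleed do not match within Protocol 8.1, and must be reconciled.

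**What to change.** In SAP 10.7.2, for the subject's rating of efficacy:

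- Use all treated bleeding episodes as the denominator, overriding the SAP 10.1 default.
- Show a 'not rated' row beside the four categories, overall, by phase and by age group.
- Add a sensitivity table that counts with 'Poor' any treated bleed that was unrated or never reported as resolved, and any bleed that needed another factor IX product.

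This uses data already collected and needs no protocol amendment. The costs are a few lines of SAP text, one extra table and a possibly lower reported success percentage. The sensitivity table is a deliberate worst case and should be labelled so.

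In Protocol 8.1, reconcile the infusion-level contact trigger with the per-episode rating, so that the text states which rating the trigger refers to and when it is recorded. That is a wording change, to be made through the amendment process in Protocol 13.2.

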8.2. Investigator's Assessment of Efficacy

At each study visit [during Treatment Phase and Continuation Phase; see Table 1], the investigator will make an assessment of APVO101 prophylaxis efficacy and an assessment of efficacy for control of bleeding episodes [if bleeding episode(s) are reported by the subject and/or their parent or legal guardian during the period]. The assessment will be based on the recording of events in the diary (i.e., review of subject diary) and discussion with the study subject and/or their parent or legal guardian.

The investigator will indicate the overall assessment of APVO101 prophylaxis efficacy, considering the absence of bleeding episodes, site, severity and types of bleeding episodes treated, and other factors that might influence the therapeutic response. In addition, when bleeding episode(s) are reported by the subject and/or their parent or legal guardian, the investigator will also rate the APVO101 efficacy for control and management of bleeding episode(s) treated. The investigator will consider the site, severity and type of the bleeding episodes reported by the subject and/or their parent or legal guardian when evaluating efficacy of APVO101 for control and management of bleeding episodes.

The investigator's efficacy assessment categories for prophylaxis and control of bleeding episodes will include: 'effective', 'partially effective' and 'not effective'.

If, in the estimation of the investigator, the response has been sub-optimal (i.e., an occurrence of 'poor' or 'no response' to the therapy for a specific bleeding episode as reported by the subject and/or their parent or legal guardian), this will be recorded and the reason for this assessment will be specified. In such an event (sub-optimal response), the investigator will review the circumstances surrounding the bleed and its response to therapy. Information collected shall include the following:

- Site of the bleed
- Cause and extent of injury
- Past history of bleeds at the anatomical site (determined by the investigator from subject's medical and hemophilia-related history and from the review of subject's diary while on study)
- Relevant clinical issues at the site for that bleed (e.g., in the case of a joint bleed, if the joint is a target joint, the extent of pain, joint swelling, and dysfunction over time (determined by the investigator from subject's medical and hemophilia-related history)
- Specifics of the management administered to that point

If a sub-optimal response to treatment is observed in two separate bleeding episodes in the same subject over the course of the study, this will be reported as an AE, although the investigator will have the option of reporting a sub-optimal response to one bleed as an AE.

In the case of a sub-optimal response, the investigator is encouraged to perform a test for inhibitory factor IX antibodies and APVO101 recovery (75 ± 5 IU/kg; factor IX measurements pre-infusion and at 15-30 minutes post-infusion). Samples for APVO101 recovery determination will be processed locally and tested locally and by the central laboratory.

The test for inhibitory factor IX antibodies will be completed locally and by the central laboratory. A repeat test will be performed by the central laboratory in case of a positive inhibitor test result by the central laboratory within 2 weeks of the study site notification of the original positive local laboratory result. Subjects who develop an inhibitor that changes from a low (≤ 5 BU) to a high titer (> 5 BU) inhibitor or from a high titer to a low titer upon a second evaluation should return to the study site within two weeks of the second inhibitor assessment, for a third inhibitor test with a suggested minimum wash-out period of 72 hours. Once a low (0.6 to 5 BU) or a high titer (> 5 BU) inhibitor is confirmed, the subject will be withdrawn from the study. Any inhibitor confirmed by the central laboratory must be reported as a serious adverse event (SAE).

8.3. Surgeon's Assessment of Efficacy

APVO101 will be evaluated for success in providing coverage for surgical procedures (if required during Treatment/Continuation phases of the study). This will be assessed by the surgeon as follows:

- Estimation of expected blood loss prior to surgery (prior to infusion of APVO101), and actual blood loss during surgery, at the end of surgery, 12 hours and 24 hours post- surgery or every 12 hours for at least 3 days post-surgery or until healing in case of a major surgery, as 'less than expected', 'expected', or 'more than expected'
- Estimation of blood loss post-surgery at 12 hours and 24 hours post-surgery or every 12 hours for at least 3 days post-procedure or until healing in case of a major surgery, as 'hemostasis superior', 'hemostasis adequate', or 'hemostasis poorly controlled'

The surgeon will estimate the expected blood loss at the time of surgery (prior to infusion of APVO101) by taking into consideration the planned surgical procedure in a hemostatically normal male individual of the same demographics as the study subject for the intra-operative period, and, if applicable, for the post-operative period until drain removal and/or healing.

During the surgery, the surgeon should evaluate blood loss as per standard of care for the surgical procedure and the discretion of the surgeon.

At the end of the surgery, the surgeon will assess total blood loss for the surgical procedure and record the use of blood products for the duration of the surgical procedure (if applicable).

The use of and volume of blood products during the perioperative period (first 24 hours) and during the healing phase (see [Table 3](#)) will be recorded as an indicator of APVO101 hemostatic efficacy.

9. ASSESSMENT OF SAFETY

Safety throughout the clinical trial will be evaluated by assessment of the following:

- Adverse events (AEs)
 - All AEs will be reported by investigators and subjects and/or their parent or legal guardian. AEs are to be elicited by the investigator (or designate) asking the subject and/or their parent or legal guardian non-leading questions. Subjects and/or their parent or legal guardian will record AEs in the subject diary and the information will be reviewed by the investigator during each scheduled visit.
- Physical exams
- Vital signs (pulse rate, blood pressure, respiratory rate and temperature)
- Laboratory assessments, including:
 - Thrombogenic markers (D-dimer, TAT complex and fragment 1+2)
 - Serum chemistry (ALT, AST, ALP, BUN or urea, uric acid, creatinine, total bilirubin and glucose)
 - CBC with differential [hemoglobin, hematocrit, absolute counts of: white blood cells, neutrophils, monocytes, lymphocytes, eosinophils, basophils, platelets and red blood cells; mean platelet volume (MPV), mean corpuscular volume (MCV), mean corpuscular hemoglobin (MCH) and mean corpuscular hemoglobin concentration (MCHC)]
 - Urinalysis [urine dipstick, followed by microscopy if abnormal]
 - Immunogenicity (inhibitor titer, non-inhibitory factor IX binding antibodies, and anti-CHOP antibodies)

Any clinically significant changes (as determined by the investigator) in laboratory test results, vital signs or physical exam must be captured as adverse events.

The above listed safety assessments will be evaluated at pre-determined time points during the conduct of the trial (see Table 1 and [Table 3](#)).

The central laboratory will create a distribution of values for all three thrombogenic markers (D-dimer, TAT complex, and fragment 1+2) based on negative controls (human plasma). The cut-off point for positivity will be defined as any value beyond the 99th percentile of the distribution of values for the negative controls for that particular parameter.

